#### 7.3 Treatment phase

The treatment phase will begin at the time of allocation of the first subject and will consist of the study treatment cycles. The treatment phase will end when the last patient discontinues the study drug. Prior to the completion of the final primary study analysis, an individual subject will remain in the treatment phase until documentation of disease progression.

Subjects who discontinue study drug administration prior to disease progression will continue to be followed in the treatment phase according to the tumor assessment schedule listed in table 3 (performed at week 6 after the first dose of study drug and then, every 12 weeks or sooner if clinically indicated) until documentation of disease progression or start of another anticancer therapy.

Subjects will be allocated in each primary tumor cohort to receive lenvatinib 24 mg by continuous once daily oral administration. Subjects will undergo safety and efficacy assessment as defined in Table 3. Other reasons for discontinuation of study drug different from disease progression include development of unacceptable toxicity, withdrawal of consent or sponsor discontinuation of lenvatinib development.

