## Cycle 1/Day 7 (Visit 4)

- Obtain vital signs (BP, HR, RR and body temperature at rest) and weight
- Evaluate ECOG performance status.
- Perform a comprehensive physical examination (including a neurological evaluation). A symptom-directed physical examination will be performed at any time during the study, as clinically indicated.
- Instruct the subject not to take the Day 15 dose of study drug before coming to the site.
- Collect blood samples for biochemistry and hematology analyses (see Table 5 for the tests to be performed).
- Collect urine sample and perform urinalysis (see Table 5 for the tests to be performed).
   Repeat complete full blood count with differential and perform AEs assessment as per the investigator judgment (until improvement to < Grade < 3). A delay of study treatment for more than 28 days (due to AE) will require a discussion with the sponsor who will probably determine to discontinue the subject.

- · Record concomitant medication use.
- Record any AEs or SAEs.

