## 20.2 Analysis Sets

The analysis sets will be defined as follows:

- Full Analysis Set will include all allocated subjects. This will be primary analysis set for the
  efficacy endpoints.
- Per Protocol Analysis Set will include those subjects who were allocated and received at least one dose of the assigned study drug and had no major protocol deviations. The subjects will complete both baseline and at least one post-baseline tumor assessments (week 6).
- Safety Analysis Set will include all subjects who were allocated and received at least one
  dose of the study drug and had at least one post-baseline safety evaluation (week 6). This
  will be the analysis set for all safety evaluations.
- Pharmacodynamic Analysis Set: All the subjects who have received at least one dose of study drug and have evaluable pharmacodynamic data.

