## 20.10 Adverse events

Adverse events will be graded using CTCAE v4.3. Investigators will collect all adverse event CTCAE grades (for both increasing and decreasing severity). Adverse events will be classified into standardized medical terminology from the verbatim description (investigator term) using the Medical Dictionary for Regulatory Activities (MedDRA). Adverse events will be presented by preferred term (PT) nested within system organ class (SOC). Verbatim descriptions and MedDRA SOC and PT for all adverse events will be contained in the data listings of the clinical study report for this protocol.

An overview table, including the incidence of and the number of subjects with TEAEs, SAEs, deaths, and those TEAEs that led to study drug discontinuation, dose modification, or dose interruption will be provided. The incidence of TEAEs will be summarized by SOC, PT, CTCAE grade, and relatedness to study drug. All summaries will be performed by cohort. Although a MedDRA term may be reported more than once for a subject, that subject will be counted only one time in the incidence count for that MedDRA term with the highest CTCAE grade (in the summary by CTCAE grade) or with the closest relationship to study treatment (in the summary by relatedness to study treatment). TEAEs will be defined as adverse events that emerge during treatment, having been absent pretreatment (at baseline) or those that:

- Reemerge during treatment, having been present at baseline but stopped prior to treatment, or
- Worsen in severity during treatment relative to the pretreatment state, when the adverse event is continuous.

Separate summary tables will be provided for: all TEAEs, treatment-emergent SAEs, TEAEs reported as treatment-related, treatment-emergent SAEs reported as treatment-related, and TEAEs leading to treatment discontinuation.

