4.3 Exploratory objective(s) and variables

The exploratory objectives are:

- To evaluate biochemical response (changes in CgA, 5-HIAA and NSE levels) and its association with response rate and progression-free survival.
- To assess whether baseline tumor and blood biomarkers may be predictive of response to lenvatinib.
- To explore additional hypotheses related to biomarkers and relationship to lenvatinib, neuroendocrine tumors, other endocrine disorders and/or cancer which may arise from internal or external research activities.

Exploratory variables:

- The changes in tumor markers (CgA, 5-HIIAA and NSE) will be analysed by cohort and significant reductions defined as 50% reduction or more regarding the baseline values will be calculated.
- The relationship between reductions and PFS and radiological response will be assessed.

EudraCT number: 2015-001467-39

Confidential Version 2.0

Page 10 of 16 Date: June 04, 2020

The second and third exploratory objectives will be assessed in the final analysis not in the interim analysis. According to the biomarkers that are available, the analysis of these objectives will be specified.

5. Study populations

The analysis sets will be defined as follows:

- Full Analysis Set will include all allocated subjects. This will be primary analysis set for the efficacy endpoints.
- Per Protocol Analysis Set will include those subjects who were allocated and received at least one dose of the assigned study drug and had no major protocol deviations. The subjects will complete both baseline and at least one post-baseline tumor assessments (week 6). Experior will send a list of major protocol deviations to establish the per-protocol set after the close out of data base. The PI ([name]) will decide which patients should be excluded to define the per protocol analysis set.
- Safety Analysis Set will include all subjects who were allocated and received at least one dose of the study drug and had at least one post-baseline safety evaluation (week 6). This will be the analysis set for all safety evaluations.

6. Statistical strategy

Below are detailed the statistical aspects of the data analysis.

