6.2.1 Summary statistics

Secondary endpoints will be summarized with descriptive statistics. Continuous variables will be summarized with n, NA, mean, standard deviation, median and range. Frequency counts and percentage of subjects within each category will be provided for categorical data.

First secondary objective:

Safety analyses will be based on the Safety Analysis Set. All safety analyses will be summarized separately by cohort.

Adverse events will be classified into standardized medical terminology from the verbatim description (investigator term) using the Medical Dictionary for Regulatory Activities (MedDRA). Adverse events will be presented by preferred term (PT) and by system organ class (SOC).

Echocardiogram results (LVEF), and their changes from baseline will be summarized using descriptive statistics. Prolongation of QTc will be analysed using descriptive statistics and frequency tables.

The degree of exposure (dose, duration of treatment, interruptions/reductions of dose) will be assessed to determine the degree to which study safety can be assessed. These results will be presented with descriptive statistics (n, NA, mean, standard deviation, median and range).

Second secondary objective:

The ETS and DpR will be calculated for each cohort. Both ratios will be calculated using the total sum of diameters provided in tumor assessments by central radiology review.

Third secondary objective:

PFS will be calculated using start date of study drug and progression disease or death date (whichever occurs first), based on the Full Analysis set and Per-protocol Analysis Set. PFS censoring rules will follow FDA guidance in 2007 (see Table A).

OS will be calculated using start date of study (C1D1).

A Kaplan Meier survival analysis will be carried out to analyse PFS, providing the median and the corresponding 95% CI of time to progression. Survival curves will be reported.

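### The Safety Analysis Set requires a post-baseline evaluation tagged week 6, so as written treated patients who die before week 6 are left out of the summary safety tables

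*SAP*

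**What the plan says.** SAP Section 5 defines the Safety Analysis Set as allocated subjects who "received at least one dose of the study drug and had at least one post-baseline safety evaluation (week 6"). Protocol Section 20.2 imposes the same condition: "had at least one post-baseline safety evaluation (week 6"). Both documents make this the set for every safety evaluation, and SAP Section 6.2.1 repeats it: "Safety analyses will be based on the Safety Analysis Set. All safety analyses will be summarized separately by cohort". Protocol Section 20.8 says the same. No other set of treated patients is named for adverse events or deaths.

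The tables affected are described in protocol Section 20.10. The overview table reports "the number of subjects with TEAEs, SAEs, deaths, and those TEAEs that led to study drug discontinuation", among other items. The same section keeps full listings: "Verbatim descriptions and MedDRA SOC and PT for all adverse events will be contained in the data listings".

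The visit schedule (protocol Section 13.1, Table 4) labels Visit 7, Cycle 2 Day 15, as week 6. Safety is assessed before then, at Cycle 1 Day 7, Cycle 1 Day 15 and Cycle 2 Day 1. The instruction at Cycle 1 Day 7, for example, is "Record any AEs or SAEs".

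**The concern.** A safety set should be fixed by exposure. Here membership also depends on something that happens after dosing, and a patient can fail the condition because of the very outcome the tables are meant to count. A patient who is dosed and dies in week 3 has had safety data collected but cannot have a week 6 evaluation.

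Safety and tolerability is the first secondary objective and is reported as rates within each cohort. There is no control arm, so these rates are the main safety summary, and at 55 patients per cohort a few exclusions move them visibly. The plan is also uneven: SAP Table A counts a death before the first progression assessment as a PFS event, while the safety rule would leave the same death out of the safety tables.

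**Working it through.** **Inputs**
- Membership rule: SAP Section 5 and protocol Section 20.2.
- Cohort size: 55 (protocol Sections 9 and 20.6).
- Week 6 visit: Cycle 2 Day 15, with 28-day cycles.
- Number of deaths or early stops before week 6: not given in either document. All counts below are assumptions.

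**The plan's own figure.** The rule has no figure of its own. The 55 used as denominator is sound: for 10% against 25%, an exact one-sided binomial test that needs at least 10 responses in 55 has alpha 0.0444 and power 0.911. With 54 patients and the same cut-off the power is 0.899.

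**Step 1: when week 6 falls.** Cycle 2 Day 15 is day 28 + 15 = 43. The three scheduled treatment visits between the first dose and day 43 (Cycle 1 Day 7, Cycle 1 Day 15, Cycle 2 Day 1) all record adverse events.

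**Step 2: deaths before week 6, rule read literally.** With k deaths before week 6 and j later, the all-treated rate is (k + j)/55. The tabulated rate is j/(55 − k).

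| k | j | All treated | As written |
|---|---|---|---|
| 1 | 0 | 1/55 = 1.8% | 0/54 = 0% |
| 2 | 0 | 2/55 = 3.6% | 0/53 = 0% |
| 3 | 0 | 3/55 = 5.5% | 0/52 = 0% |
| 5 | 0 | 5/55 = 9.1% | 0/50 = 0% |
| 1 | 2 | 3/55 = 5.5% | 2/54 = 3.7% |
| 2 | 1 | 3/55 = 5.5% | 1/53 = 1.9% |
| 2 | 3 | 5/55 = 9.1% | 3/53 = 5.7% |

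However many early deaths there are, they add nothing to the tabulated count.

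**Step 3: other event rates.** Suppose 8 of 55 stop for toxicity (14.5%) and 3 patients are excluded, e of whom had the event. The tabulated rate is (8 − e)/52:
- e = 3: 5/52 = 9.6%
- e = 2: 6/52 = 11.5%
- e = 1: 7/52 = 13.5%
- e = 0: 8/52 = 15.4%

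The rate falls only if e/3 exceeds 8/55, that is, if the excluded patients have the event more often than the cohort. With e = 0 it rises. The direction is therefore not fixed for these rates.

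**Step 4: which early stoppers are lost.** Stopping early does not by itself exclude a patient. Protocol Section 7.3 says: "Subjects who discontinue study drug administration prior to disease progression will continue to be followed in the treatment phase". Off-treatment assessments (Section 7.3.1) and adverse event follow-up (Section 14) can also supply an evaluation. If any evaluation from week 6 onward is accepted, only patients with none are lost. If the week 6 visit itself is required, more are lost. The exposure is greatest after withdrawal of consent, because Section 18.2 then stops data collection. It is also high after a very early last dose: a last dose on day 14 puts the end of the 28-day off-treatment window at 14 + 28 = day 42. That boundary is only approximate, since the assessment may come earlier in the window and visits carry a tolerance of one day either way.

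**Step 5: the looser reading.** If the tag is only a label, any post-baseline evaluation qualifies. The loss is then limited to dosed patients with none, such as a death before Cycle 1 Day 7. One such death out of 3 gives 2/54 = 3.7% instead of 3/55 = 5.5%.

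**The case against.** The strongest reply is that the literal reading is not the natural one. Asking for at least one evaluation makes little sense if only one visit can count, and three safety visits come before week 6. The Per Protocol definition just above carries the same tag: subjects must "complete both baseline and at least one post-baseline tumor assessments (week 6"). There it fits, because week 6 is the first tumor assessment, so it may simply have been carried over. This is plausible, but neither document says so. Two programmers could build different sets from the same sentence, and under the looser reading membership still depends on what happens after dosing.

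A second reply is that protocol Section 12.5 treats the recording of adverse events as safety assessment, so a fatal event recorded after dosing might itself count as the required evaluation. That would rescue some patients under the looser reading. It does not cover every death, because Section 14 says disease progression is not to be recorded as an adverse event, and it does not supply a week 6 evaluation.

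Third, the consequence is limited. Recorded events stay in the listings, serious events are reported separately, and early deaths count in PFS and in OS measured from Cycle 1 Day 1. The study is exploratory, safety is descriptive, and ORR on the Full Analysis Set is untouched. All of this stands. It limits the problem to the summary safety rates but does not remove it.

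**Conclusion.** The concern holds. As written, a treated patient who dies before Cycle 2 Day 15 is outside the only safety set and is missing from the overview table. The direction is certain for early deaths: they contribute zero. For other events the bias can go either way. The size rests entirely on assumed counts: with 3 deaths in 55, of which 1 or 2 occur before week 6, the tabulated rate is 3.7% or 1.9% instead of 5.5%. If the tag was meant loosely, the loss is smaller but not nil. This should be fixed because it affects the summary rates of a secondary objective. It does not threaten the primary endpoint.

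**What to change.** In SAP Section 5 and protocol Section 20.2, define the Safety Analysis Set as all subjects who received at least one dose of lenvatinib, and delete the clause requiring a post-baseline safety evaluation at week 6. Use available-case denominators only for change-from-baseline summaries of laboratory values, vital signs, ECG and LVEF, and state n for each. This removes the selection under either reading of the tag.

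The cost is one clause in the SAP and no new data. The protocol text needs a written change approved by the sponsor under Section 17.1; otherwise the SAP should document its departure from Section 20.2. Some reported adverse event rates may be slightly less favourable.

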6.1 Primary analysis

All efficacy analyses will be based primarily on the Full Analysis Set and secondarily on the Per Protocol Analysis Set.

6.1.1 Summary statistics

The ORR will be calculated by RECIST v1.1 upon central radiologic assessment, independently for each cohort.

Waterfall plots (2D and 3D) will be calculated to examine the changes in tumor lesions from baseline.

6.1.2 Statistical inference

It is not planned statistical inference.

Page 11 of 16 Date: June 04, 2020

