#### 20.6 Sample Size and Accrual

Sample size has been calculated using single stage design. For considering Lenvatinib as an effective treatment, a success rate of ORR of at least 25% is expected. However, a success rate of 10% or less would be considered unacceptable. With 90% power and a 5% level of significance, a total of 55 patients for each cohort are required.

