#### 20.7 Data Analyses Plans

Summary tables (descriptive statistics and/or frequency tables) will be provided for all baseline variables, efficacy variables, and safety variables, as appropriate. Continuous variables will be summarized with descriptive statistics (n, NA, mean, standard deviation, median and minimum and maximum values). Ninety-five (95) percent confidence intervals may also be presented, as appropriate. Frequency counts and percentage of subjects within each category will be provided for categorical data.

Missing data will be ignored.

Secondary endpoints will be summarized with descriptive statistics. Continuous variables will be summarized with n, NA, mean, standard deviation, median and range. Frequency counts and percentage of subjects within each category will be provided for categorical data. Multivariate regression models may be used to study relations between explanatory variables and primary endpoint. Survival analysis will be performed to analyze PFS, Kaplan & Meyer curves will be presented and possible comparisons will be tested using the log-rank test or the Cox proportional hazard model for multivariate analysis.

Patients with lost of follow-up or treatment discontinuation will be included in the final analysis of primary endpoint if they have at least one tumor assessment and considered as censored data for survival endpoints.

Page 77 of 88 Date: April 04th, 2016

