6.8 Statistical significance level

A significance level of 5% will be considered.

Page 15 of 16 Date: June 04, 2020

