6.11 Handling of missing data

No planned procedure of imputation of missing values. The analysis will be performed with the available data.

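### The SAP plans no inference for the primary ORR, so the 10% versus 25% test that gave 55 patients per cohort has no analysis, responder threshold or committed interval

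*SAP*

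**What the plan says.** **Design.** Protocol 20.6 describes a single-stage calculation. An ORR of 10% or less is unacceptable, and the target is worded: "For considering Lenvatinib as an effective treatment, a success rate of ORR of at least 25% is expected". The result is: "With 90% power and a 5% level of significance, a total of 55 patients for each cohort are required". It names no test, no sidedness and no minimum number of responders.

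**Analysis.** Protocol 20.1 leaves the detail to the SAP. Protocol 20.5.1 fixes the timing, the separate analysis by cohort and the central review. SAP 6.1.1 calculates ORR per cohort and adds waterfall plots. SAP 6.1.2 then reads "It is not planned statistical inference".

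**Intervals and level.** Protocol 20.7 is permissive and does not mention ORR: "Ninety-five (95) percent confidence intervals may also be presented, as appropriate". SAP 6.8 says "A significance level of 5% will be considered", without tying the level to an endpoint. The only interval the SAP commits to is for the PFS median (6.2.1), a secondary endpoint.

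**Denominator.** Protocol 20.2 says "Full Analysis Set will include all allocated subjects" and makes that set primary for efficacy. SAP 4.1 divides by the total of patients. Protocol 20.7 says that patients lost to follow-up or off treatment "will be included in the final analysis of primary endpoint if they have at least one tumor assessment". SAP 6.11 says "The analysis will be performed with the available data".

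**The concern.** Power and significance level are properties of a decision rule. The protocol uses both to justify 110 patients, and the SAP says the rule will not be applied. ORR can still be calculated, and anyone could compute a p-value or interval from the counts. What is missing is pre-specification: whether the test is one- or two-sided, how many responders count as success, and who is in the denominator could all be settled once the counts are known.

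The protocol does expect a verdict. Under sample collection and handling, Appendix VI lets the sponsor drop the pharmacogenomic work if, among other conditions, the primary efficacy endpoint is not achieved. Nothing defines achievement. The trial is open label, so response data accumulate in view of the study team.

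**Working it through.** **Inputs.** From protocol 20.6: p0 = 0.10, p1 = 0.25, power 0.90, significance 0.05 (sidedness not stated), n = 55 per cohort. X is the number of responders, X ~ Binomial(n, p).

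**1. Reproduce the 55.** Find the smallest n with a threshold r such that P(X ≥ r | 0.10) ≤ 0.05 and P(X ≥ r | 0.25) ≥ 0.90.

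- Exact, one-sided 5%: n = 55, r = 10. This matches the protocol.
- Exact, one-sided 2.5% (the efficacy side of a two-sided 5% test): n = 64, r = 12.
- One-sided normal approximation: 49, or 56 with continuity correction. One-sided arcsine: 53.
- Two-sided normal approximation: 59, or 65 with continuity correction. Two-sided arcsine: 65.

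Among these, only the exact one-sided 5% design gives 55.

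**2. Threshold at n = 55.**

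| Reject at | Observed ORR | P(reject), true 10% | P(reject), true 25% |
|---|---|---|---|
| ≥ 9 | 16.4% | 0.0944 | 0.955 |
| ≥ 10 | 18.2% | 0.0444 | 0.911 |
| ≥ 11 | 20.0% | 0.0189 | 0.845 |
| ≥ 14 | 25.5% | 0.0008 | 0.521 |

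Only r = 10 meets both conditions.

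**3. Sidedness.** At 10/55:

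- one-sided exact p = 0.044, which rejects 10%;
- two-sided exact p = 0.066, which does not;
- Clopper–Pearson 95% interval 9.1% to 30.9%, which contains 10%;
- Clopper–Pearson 90% interval 10.2% to 28.9%, which excludes 10%.

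At 11/55 the two-sided p is 0.022 and the 95% lower limit is 10.4%, so the approaches agree from 11 upwards. The disagreement is confined to one count. P(X = 10) = 0.9112 − 0.8446 = 0.067 at a true ORR of 25%, and 0.130 at 20%.

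**4. If 25% is read as a bar on the observed rate.** 0.25 × 55 = 13.75, so at least 14 responders are needed, with power 0.521 at a true 25%. Counts of 10 to 13 would pass the test and miss the bar. P(10 ≤ X ≤ 13) = 0.9112 − 0.5206 = 0.391 at a true 25%, and 0.487 at 20%. These figures apply only under that reading.

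**5. Denominator.** The documents do not say how many patients would have no scan, so this is shown as a range. One-sided p for 9 responders against 10%:

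| n | 55 | 50 | 49 | 48 |
|---|---|---|---|---|
| p | 0.094 | 0.058 | 0.052 | 0.046 |

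Dropping 55 − 48 = 7 or more patients turns a non-rejection into a rejection.

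**6. Two cohorts.** If both true rates are 10%, the chance of at least one false success is 1 − (1 − 0.0444)² = 0.087. This is acceptable if the cohorts are stated to be separate claims.

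**The case against.** The best defence is that this is a labelled exploratory phase II trial with the right sample size and no data lost. The rule can be recovered: the protocol, dated April 2016, fixed the single stage, 10%, 25%, 5%, 90% and 55, and those inputs point to r = 10. Sizing a single-arm study on a test and then reporting an estimate is defensible if an exact interval is committed.

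On the denominator, the Full Analysis Set is clearly primary, SAP 4.1 divides by all patients, and SAP 6.11 declines imputation without saying that unscanned patients drop out. Only one sentence in protocol 20.7 pulls the other way. The nine-responder example also needs exactly 9 responders (probability 4.3% at a true 25%, 11.3% at 20%) and at least 7 of 55 (13%) without a scan. Finally, 25% is most naturally read as the design alternative.

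Much of this limits the size of the problem. The 25% bar is a conditional reading, the two-cohort figure is incidental, and the SAP's earlier history cannot be judged from version 2.0. But no exact interval is committed, so the estimation defence is not available as written. A threshold that a reader must back-calculate is not one the plan has adopted, least of all when the SAP expressly disclaims inference. The exploratory label does not cancel a stated power.

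**Conclusion.** The concern holds and must be fixed, because it affects the primary endpoint and the trial's only powered hypothesis. SAP 6.1.2 contradicts protocol 20.6. The sample size is sound, and the gap is in pre-specification and reporting.

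On sidedness, the gap can change the conclusion at one count, 10/55, with probability 6.7% at a true ORR of 25% and 13.0% at 20%. It reaches 10 to 13 responders only if 25% is taken as an observed bar. The denominator effect depends on an unknown number of unscanned patients, and in the example needs at least 7 of 55. The figures assume exact binomial calculations with 55 patients analysed per cohort, except where the denominator is varied.

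**What to change.** Replace SAP 6.1.2 with wording such as:

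> In each cohort separately, on the Full Analysis Set of all allocated subjects and by central review, patients without an evaluable post-baseline scan count as non-responders. The hypothesis ORR ≤ 10% is tested with an exact one-sided binomial test at 5%, rejecting at 10 or more responders of 55 (exact one-sided p ≤ 0.05 if the allocated number differs). ORR is reported with exact two-sided 90% and 95% confidence intervals. The two cohorts are separate claims, each at 5%.

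The 90% interval corresponds to the one-sided 5% test, so a 10/55 result will not appear to contradict itself.

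Also:

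- State that the tumor-assessment condition in protocol 20.7 and the available-data rule in SAP 6.11 do not set this denominator.
- Clarify in protocol 20.6 that 5% is one-sided and that 25% is the design alternative, not a bar on the observed rate.
- SAP version 2.0 is dated June 2020 and the calendar planned the primary analysis for July 2017. If ORR data had been reviewed before the change, report that the rule was derived from the protocol's sample-size inputs and was not pre-specified in the SAP.

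The cost is wording in the SAP and in protocol 20.6 and 20.7, the latter by sponsor-approved written amendment or administrative change under protocol 17.1. No extra patients or data are needed.
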